8.3 Follow-up Evaluations

For participants initiating therapy or currently under treatment, a short interval follow-up will occur at 12 Weeks (\pm 2 Weeks). This is expected to coincide with planned treatments/clinical follow-up and therefore minimize unnecessary clinic visits that could increase participant burden.

8.3.1 Vital status

8.3.2 State of planned cancer therapy (initiated as planned versus delayed initiation, no initiation, or initiation of alternate therapy in place of planned therapy)

8.3.3 Optional QoL questionnaires as described in [Section 8.2.10](#):

- EORTC QLQ-C30
- SCNS-SF34

8.4 Final Evaluations, Off Study

Participants who are not currently receiving any treatment will not complete a follow-up evaluation. Therefore, the Off Study Summary Form should be completed in iMedidata Rave after completing the Enrollment Data Collection in [Section 8.2](#).

For participants who are planning to initiate therapy or are currently under treatment, at the completion of all follow-up evaluations described in [Section 8.3](#), the Off Study Summary Form should be completed in iMedidata Rave.

9.0 MEASUREMENT OF EFFECT

This is a non-interventional protocol.

The following definitions will be employed for case classification and data reporting for the primary protocol objective, to estimate the number of cancers in PWH who present for care at domestic AMC sites:

Table 9-A: Definitions for case classification and data reporting

Site-specific frequency of primary cancer cases	Total number of participants that present to the site with a first diagnosis of cancer. This encompasses cases that are in the period from histologically proven cancer to initiation of planned first-line therapy, as well as cases already receiving the planned first-line therapy for primary disease.
Site-specific frequency of recurrent cancer cases	Total number of participants that present to the site with a diagnosis of cancer within the last 5 years. This includes participants on surveillance, or best supportive care.
Site-specific frequency of prior cancer cases	Total number of participants that present to the site with a recurrent (i.e., non-primary) cancer diagnosis. This encompasses cases that are pre-treatment for recurrent disease, undergoing planned non-first-line therapy, or cases for whom no anti-cancer therapy is planned, including due to metastatic or locally advanced, inoperable disease.
Pre-treatment phase	The period in which a participant has a histologically diagnosed cancer, with cancer-specific treatment planned but not yet initiated.
Treatment phase	The period in which the participant has started therapy for cancer. This can include surgery, radiation, and/or chemotherapy. This period completes when all planned therapy has been completed within a therapeutic encounter.
First-line therapy	All therapy performed as part of a treatment plan with a new/primary diagnosis of cancer, including surgery, radiotherapy, and chemotherapy, alone or in combination.
No treatment planned	The point at which no further active cancer treatments are planned. Initiation of best supportive care or palliative care.

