3.1 Eligibility Criteria

_____ 3.1.1 Participant can understand and is willing to sign a written informed consent document.

_____ 3.1.2 HIV positive. Documentation of HIV-1 infection by means of any one of the following:

- Documentation of an HIV diagnosis in the medical record by a licensed health care provider;
- Documentation of receipt of antiretroviral therapy (ART) (i.e., at least two different medications that do not constitute a prescription for pre-exposure prophylaxis [PrEP]) by a licensed health care provider. Documentation may be a record of an ART prescription in the medical record, a written prescription in the name of the participant for ART, or pill bottles for ART with a label showing the participant's name;
- HIV-1 RNA detection by a licensed HIV-1 RNA assay demonstrating >1000 RNA copies/mL;
- Any licensed HIV screening antibody and/or HIV antibody/antigen combination assay confirmed by a second licensed HIV assay such as a HIV-1 Western blot confirmation or HIV rapid multispot antibody differentiation assay.

Note: The term "licensed" refers to a kit that has been certified or licensed by an oversight body within the participating country and validated internally (e.g., U.S. FDA).

WHO (World Health Organization) and CDC (Centers for Disease Control and Prevention) guidelines mandate that confirmation of the initial test result must use a test that is different from the one used for the initial assessment. A reactive initial

rapid test should be confirmed by either another type of rapid assay, or an E/CIA that is based on a different antigen preparation and/or different test principle (e.g., indirect versus competitive), a Western blot, or a plasma HIV-1 RNA viral load.

- _____ 3.1.3 Patient was diagnosed with or treated for cancer within the last 5 years. Participants will qualify under one of three categories:
- New, primary or recurrent diagnosis –Considering or currently receiving cancer treatment
 - Metastatic or locally advanced cancer – This includes cases for which there are no current definitive therapy options for cure (i.e., inoperable) but may be considered for non-standard / non-curative therapies.
 - Prior diagnosis (within 5 years), in remission – Not currently on cancer treatment other than ART or maintenance therapy.
- _____ 3.1.4 Age \geq 18 years.
- _____ 3.1.5 Participant presents to an AMC domestic clinical trial site for either clinical care or research.

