8.2 Enrollment Data Collection

Following informed consent, additional, identifiable data will be collected, including:

- 8.2.1 Patient characteristics: Date of birth, biological sex, gender identity, race, ethnicity, height and weight
- 8.2.2 Sociodemographic: Socioeconomic status (e.g., ZIP code, housing status [homeless y/n, categories for frequency of housing insecurity]), health insurance (insured/uninsured, type if insured)
- 8.2.3 Health behaviors: Tobacco use (type, exposure [pack/day, years use]), illicit drug use (ever, type, years exposure), alcohol use (ever, exposure [drinks/week], years exposure)
- 8.2.4 Comorbid conditions: Hepatitis B and C co-infection, cardiovascular disease (y/n, type), psychiatric conditions (y/n, type), non-cancer pulmonary conditions (y/n, type), hepatic dysfunction, hematologic abnormalities, renal dysfunction, neurologic disorders, endocrine disorders (including thyroid disorders, and diabetes)
- 8.2.5 HIV care: Current ART regimen, years of ART use, year of HIV diagnosis, history of opportunistic infections, most recent HIV viral load and CD4+T-cell count relative to participant visit).

8.2.6 Status of cancer diagnosis (one of the following):

- New diagnosis, pre-treatment phase
- New diagnosis, treatment phase
- Prior diagnosis, in remission (within 5 years of initial diagnosis or treatment)
- Prior diagnosis, recurrent, pre-treatment phase
- Prior diagnosis, recurrent, treatment phase
- Prior diagnosis, recurrent, no treatment planned

8.2.7 For participants with a new diagnosis (pre-treatment or treatment), the following will be collected:

- Cancer type, date of cancer diagnosis, method of diagnosis (clinical, cytology, histology), type of pathology performed (Hematoxylin and Eosin, immunohistochemistry, other), date of pathology, staging, staging methods (clinical, radiographic, surgical), date(s) of staging, current ECOG Performance Status (PS), current laboratory values (this would include complete blood count, renal and liver function, electrolytes)
- Cancer treatment plan: Detailed planned or current treatment. This should encompass surgical interventions, radiotherapy, and chemotherapy (agent names), including dates of planned or current therapy, and whether cancer care is being received or will occur at the enrolling institution.

8.2.8 For participants with a prior diagnosis in remission, the following will be collected:

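### Table 9-A exchanges the 'recurrent' and 'prior' labels and its 5-year class overlaps the others; separately, Section 8.2.6 has no status for a first diagnosis with no treatment planned

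*Combined protocol and SAP*

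**What the plan says.** Section 9.0 gives Table 9-A a formal role: "The following definitions will be employed for case classification and data reporting for the primary protocol objective". Three of its rows are site-specific case frequencies.

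- **Primary.** The row opens with participants presenting with a first cancer diagnosis. It then describes the time up to planned first-line therapy and the time on that therapy.
- **Recurrent.** "Total number of participants that present to the site with a diagnosis of cancer within the last 5 years". It adds: "This includes participants on surveillance, or best supportive care".
- **Prior.** "Total number of participants that present to the site with a recurrent (i.e., non-primary) cancer diagnosis". It extends to "cases for whom no anti-cancer therapy is planned, including due to metastatic or locally advanced, inoperable disease".

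Section 8.2.6 lists the statuses recorded at enrollment. One is "Prior diagnosis, in remission (within 5 years of initial diagnosis or treatment"). Three are recurrent statuses, the last being "Prior diagnosis, recurrent, no treatment planned". New diagnoses have only a pre-treatment and a treatment status.

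Section 3.1.3 admits patients diagnosed with or treated for cancer in the last 5 years. Its prior category means in remission. Its metastatic or locally advanced category is described as follows: "This includes cases for which there are no current definitive therapy options for cure (i.e., inoperable"). That category does not require recurrence.

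**The concern.** A table that governs classification should give each case one class and the right name. Here two of the three frequency rows carry each other's definition. A site or programmer working from the row labels would report remission patients as recurrent and relapsed patients as prior.

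The wording of the 5-year row also fails to separate it from the other two, so the three frequencies need not add up to the number of participants.

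A different problem arises at data capture. A patient with a first diagnosis and no planned treatment can enroll but has no matching status in 8.2.6. Correcting Table 9-A alone would not recover what was never recorded.

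**Working it through.** The plan states no figure for the recurrent or prior frequency, so there is none to reproduce. The check sets the sections side by side.

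**1. Labels**

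| Label in Table 9-A | Definition beside it | Name for that group in 3.1.3 and 8.2.6 |
|---|---|---|
| Recurrent | Any diagnosis in the last 5 years, including surveillance; recurrence not mentioned | Prior, in remission |
| Prior | Recurrent, non-primary disease | Recurrent |

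No reading of the two rows reconciles them with the other sections. Each label sits in the same row as its definition, so a fault in the text extraction is an unlikely explanation.

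**2. Overlap and omission.** The 5-year row has no condition on remission, so a primary or recurrent case diagnosed within 5 years also meets it. The row also counts diagnosis only. The opening of 3.1.3 and the remission status in 8.2.6 both accept treatment within 5 years as an alternative, so a remission patient diagnosed earlier but treated within the window meets 8.2.6 and not the Table 9-A row.

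**3. Effect on one site (assumed counts).** Take 30 first diagnoses, 10 recurrent and 20 in remission, 60 in all.

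- Labels exchanged, no overlap: 'recurrent' is reported as 20 and 'prior' as 10. The reported-to-true ratio for recurrent is 20/10 = 2.0. Primary (30), recurrent plus prior (30) and the total (60) do not change.
- Overlap read literally, all 60 diagnosed within 5 years: the 5-year row holds 60, and the three rows sum to 30 + 60 + 10 = 100 for 60 people.

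Under a pure exchange the ratio is remission/recurrent. Assumed counts of 40 and 5 give 8.0; 15 and 15 give 1.0; assumed shares of 20% and 30% give 0.67. The error can therefore go either way.

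**4. What does not depend on the split.** Section 10.1.2 counts new and existing cases per month and percentages by four cancer groups. Table 10-A follows from the cancer-group proportions alone, as p ± [1.96·√(p(1−p)/n) + 1/(2n)]. For p = 0.125 and n = 360 this gives 8.9–16.1%, as printed. Neither uses the recurrent/prior split.

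**5. Missing status.** Section 8.2.6 crosses recurrent disease with three treatment states and new disease with two. The missing cell is a new diagnosis with no treatment planned. The reason for no therapy is asked in 8.2.9 (recurrent) and not in 8.2.7 (new). For scale only, assume half of enrollees are first diagnoses and 2% to 20% of those have no treatment planned:

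- n = 360: 360 × 0.5 × 0.02 = 3.6, to 360 × 0.5 × 0.20 = 36
- n = 720: 720 × 0.5 × 0.02 = 7.2, to 720 × 0.5 × 0.20 = 72

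The documents give neither share.

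**The case against.** The strongest reply is that little rests on these labels. The primary endpoint is the number of cancers, analyzed by cancer group, and nothing in Section 10.1 or 10.2 calls for a recurrent/prior split. The definitions stand beside the labels, so a careful reader would notice the mismatch. Section 8.2.6 labels its statuses consistently, so the correct split can be tabulated for enrolled participants. All of this stands. It limits the harm but does not make the table right: Section 9.0 still says these definitions will be used for the primary objective, and 10.1.2 does not define new or existing in their place.

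A second reply is that an untreated first diagnosis does have a home in Table 9-A. The primary row opens without any treatment condition, the 5-year row mentions best supportive care, and 'no treatment planned' has its own row that is not limited to recurrence. Table 2-A also lists metastatic or inoperable cancer as a status without requiring recurrence, and best supportive care among planned treatments. This stands too. Table 9-A is ambiguous for such a case; it does not exclude it. The firm omission is in 8.2.6. A reader might infer that these patients will be coded as recurrences, because the only status with no treatment planned is a recurrent one. No section directs that, and Table 9-A describes recurrent disease as non-primary.

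**Conclusion.** The point holds in a limited form. Table 9-A is wrong as written: two labels are exchanged, and the 5-year class overlaps the primary and recurrent classes while missing some remission patients. If it is applied literally, the site-specific recurrent and prior frequencies are mislabelled. The cancer-group counts, Table 10-A and the overall totals are not affected. The split for enrolled participants can largely be rebuilt from 8.2.6, apart from the missing status.

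Three stronger readings are not supported.

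- A reader might infer that the primary estimates themselves are wrong. They do not use the split.
- A reader might put a factor on the error. Assuming 40% in remission and 15% recurrent among 720 gives 288/108 = 2.7, and 30% and 25% give 216/180 = 1.2. Those shares are not in the documents, other shares reverse the direction, and the calculation ignores the overlap.
- A reader might infer that later trials will be sized on the relapsed population. Section 10.1.1 says only that the estimated numbers of cancers will inform target populations.

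The missing status in 8.2.6 is a separate and firm gap. Its size is unknown.

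**What to change.** - **Labels.** Swap the two labels in Table 9-A so that they agree with 3.1.3 and 8.2.6.
- **Classes.** Define prior as: diagnosis or treatment within 5 years, currently in remission, neither on first-line therapy nor recurrent. The three classes are then mutually exclusive. The mention of best supportive care in the 5-year row has to be reconciled with this, as has the maintenance therapy that 3.1.3 allows in its remission category.
- **Status list.** Add 'New diagnosis, no treatment planned' to 8.2.6, add the reason for no therapy to 8.2.7 as in 8.2.9, and name the case in the primary row of Table 9-A.

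The cost is a protocol amendment, which under Section 12.2 needs CTEP and CIRB approval, plus one CRF response option with its reason item. Records entered before the change would lack the new option, so it is worth most if added early. The label and definition changes need no new data.

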10.0 STATISTICAL CONSIDERATIONS

10.1 Study Design/Endpoints

This is a non-interventional protocol. This study will utilize a prospective design to identify the frequency of new and existing cancer cases among PWH receiving care at AMC clinical trial sites.

10.1.1 Primary endpoint

The primary endpoint is to estimate the number of cancers in PWH who present for care at domestic AMC sites. These estimates will help to inform the target populations for subsequent AMC clinical trials.

10.1.2 Primary endpoint analysis

For each cancer group listed below, the number of new and existing cases per month will be estimated using a 95% Poisson confidence interval. Additionally, the distribution of cancer types will be computed as percentages and compared to the cancer type distribution in the HIV/AIDS Cancer Match (HACM) Study, a nationally representative HIV and cancer linkage database [4]. For reference, the HIV/AIDS Cancer Match (HACM) Study estimated that the proportion of participants with the following cancer types as:

1. Solid organ tumors associated with human papillomavirus (HPV) infection = 12.5%
2. Solid organ tumors unrelated to HPV = 49.3%
3. Kaposi sarcoma = 10.9%
4. Hematologic malignancies = 27.3%

10.2 Sample Size/Accrual Rate

10.2.1 Target accrual is 20 participants per month, with a target of 720 participants enrolled over 36 months. Because the primary objective's focus is estimation, we note below in [Table 10-A](#) both the width of the 95% confidence intervals (CIs) for prevalence, and the accompanying estimated case counts, for the minimum and maximum target sample sizes of 360 and 720. For each cancer group, anticipated prevalence estimates are based on those observed in other national datasets (see [Section 10.1.2](#) above). 95% CIs are computed using PASS 2021 software, utilizing a simple asymptotic estimation approach (i.e., a normal approximation to the binomial approach with a continuity correction.)

Table 10-A: Estimated case counts

Cancer Types	Sample Size of 360		Sample Size of 720	
	Prevalence	Case Count	Prevalence	Case Count
Solid Organ Tumors Associated with HPV	12.5% (95% CI: 8.9-16.1%)	45 cases (95% CI: 32-58 cases)	12.5% (95% CI: 10.0-15.0%)	90 cases (95% CI: 72-108 cases)
Solid Organ Tumors Unrelated to HPV	49.3% (95% CI: 44.0-54.6%)	177 cases (95% CI: 158-197 cases)	49.3% (95% CI: 45.6-53.0%)	355 cases (95% CI: 328-382 cases)
Kaposi Sarcoma	10.9% (95% CI: 7.5-14.3%)	39 cases (95% CI: 27-52 cases)	10.9% (95% CI: 8.6-13.2%)	78 cases (95% CI: 62-95 cases)
Hematologic Malignancies	27.3% (95% CI: 22.6-32.0%)	98 cases (95% CI: 81-115 cases)	27.3% (95% CI: 24.0-30.6%)	197 cases (95% CI: 173-220 cases)

One example of how this will translate into monthly enrollment targets is provided here: If 355 participants with solid organ tumors unrelated to HPV are to be enrolled across 36 months, or 9.9 such participants per month, the 95% CI would be 9.1-10.6 cases (i.e., 9-11 participants) per month.

- 10.2.2. The goal is to open this protocol at $\geq 75\%$ of domestic AMC sites. Based on updated responses from 19 domestic AMC sites on the protocol-associated feasibility survey, 16 AMC domestic sites indicated that this study would be feasible to open. The table below ([Table 10-B](#)) includes results for those 16 domestic sites. Based on their estimates for annual number of cancers seen at their AMC site, we anticipate that this protocol will meet accrual targets.

Table 10-B: AMC domestic site annual numbers of cancers in PWH

AMC Site	Kaposi Sarcoma	Heme Malignancies	HPV+ Solid Tumors	Non-HPV Solid Tumors	Total Cancers
LSUHSC	10	30	10	50	100
Anal Dysplasia Clinic MidWest	0	0	1	0	1
Penn	25	10	10	10	55
Wash U	30	10	15	30	85
Laser Surgery	2	3	10	0	15
MSK	5	8	5	5	23
Montefiore	2	15	15	15	47
Moffitt	3	20	15	20	58
Boston Medical Center	8	8	15	15	46
Virginia Mason	7	3	4	4	18
Miami Cancer Institute	5	30	25	25	85
George Washington	2	5	10	10	27
Puerto Rico	2	4	4	2	12
UCSF	2	1	5	3	11
UCSD	32	59	23	52	166
UNC	4	4	2	4	14
Total	139	210	169	245	763

The above estimates indicate that sites, including those with a history of consistent enrollment onto AMC trials and new sites added in current AMC grant years, see 763 cancer cases with underlying HIV infection each year. Even with a conservative patient participation rate for this minimal burden study, the protocol chairs deem the target accrual range (360-720) to be feasible.

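### The pooled cancer-type shares are not protected against uneven enrollment between sites with very different case mix, so they can misstate the mix presenting for care and blur the comparison with HACM

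*Combined protocol and SAP*

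**What the plan says.** The primary objective (Section 1.1) concerns cancers in people with HIV presenting at domestic AMC sites. Section 10.1.2 plans a 95% Poisson interval for monthly cases in each of four cancer groups. It adds that "the distribution of cancer types will be computed as percentages and compared to the cancer type distribution in the HIV/AIDS Cancer Match (HACM) Study". It names no test or interval for that comparison, and no site term, stratum or weight.

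Section 10.2.1 gives "both the width of the 95% confidence intervals (CIs) for prevalence" and the matching case counts "for the minimum and maximum target sample sizes of 360 and 720". The intervals are obtained by "utilizing a simple asymptotic estimation approach (i.e., a normal approximation to the binomial approach with a continuity correction", applied to everyone as one sample.

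On sites, Section 10.2.2 says "The goal is to open this protocol at $\geq 75\%$ of domestic AMC sites"; 16 of 19 survey respondents called the study feasible. Table 10-B lists those 16 with annual caseloads from 1 to 166. Its columns run Kaposi sarcoma, hematologic, HPV-related solid, other solid, total; the largest row is "UCSD 32 59 23 52 166".

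Section 8.1 sets up a screening list that records cancer type before consent. These data are kept apart from the enrolled data. The one comparison Section 8.1 names for them is with enrolled numbers at each site, to estimate the consenting proportion.

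**The concern.** A pooled share of enrolled participants estimates the mix presenting for care only if each site enrolls about the same fraction of its patients, or if the sites have similar mixes. The second condition fails in the plan's own table, and nothing in the plan secures the first.

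If a site with much Kaposi sarcoma enrolls vigorously and another hardly at all, the pooled share moves although the patients presenting have not changed. The binomial interval contains no allowance for this, and a larger sample does not help, because the interval shrinks while the bias stays. A gap from HACM could then partly reflect which sites enrolled more. Section 10.1.1 says the estimates will inform the target populations of later AMC trials, so the mix has practical consequences.

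**Working it through.** **1. The plan's figures reproduce.** The formula is p ± [1.96·√(p(1−p)/n) + 1/(2n)]. For Kaposi sarcoma, p = 0.109 (Section 10.1.2):
- n=720: 0.109 ± (0.0228 + 0.0007) gives 8.55 to 13.25%; Table 10-A has 8.6 to 13.2%.
- n=360: 0.109 ± (0.0322 + 0.0014) gives 7.54 to 14.26%; Table 10-A has 7.5 to 14.3%.

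All eight intervals agree within 0.1 point. They are simple-random-sample intervals.

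**2. Site mixes differ.** Table 10-B totals 139 Kaposi sarcoma, 210 hematologic, 169 HPV-related and 245 other solid tumors, 763 in all. Kaposi sarcoma is 25/55 (45%) and 30/85 (35%) at two sites, against 5/85 (6%) and 3/58 (5%) at two others. The site-by-type chi-square is 151 on 45 df (p about 2e-13). Restricted to the 10 sites with at least 20 cases, it is 117 on 27 df.

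**3. There is room for uneven enrollment.** Three years at 763 a year is 2,289 cases. 360/2,289 = 16% and 720/2,289 = 31%.

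**4. Illustration.** The caseload-weighted Kaposi sarcoma share is 139/763 = 18.2%.
- If the 25/55 and 30/85 sites enroll at half the rate of the others: (84 + 27.5)/(623 + 70) = 16.1%.
- If they enroll at twice the rate: (84 + 110)/(623 + 280) = 21.5%.
- If they do not open: 84/623 = 13.5%, a shift of 4.7 points. The Table 10-A half-width at n=720 is 2.3 points.

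**5. Effect on coverage, 16 sites fixed.** Let site enrollment fractions vary independently with coefficient of variation CV. The CV is an assumption; the documents give none. To first order, the standard deviation (SD) this adds to the pooled share is CV × √[Σ(xᵢ − p·mᵢ)²]/N, where xᵢ is the site's Kaposi sarcoma count, mᵢ its caseload, p = 0.182 and N = 763. The sum is about 742, so the factor is 27.2/763 = 3.57 points. The added SD is 1.07 points at CV 0.3 and 1.78 at CV 0.5.

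| n | Binomial SE | Half-width at p=18.2% | Total SD, CV 0.3 / 0.5 | Approximate coverage |
|---|---|---|---|---|
| 360 | 2.03 | 4.12 | 2.29 / 2.70 | 93% / 87% |
| 720 | 1.44 | 2.89 | 1.79 / 2.29 | 89% / 79% |

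Total SD is √(SE² + added SD²); coverage is 2Φ(half-width/total SD) − 1. Simulation with gamma-distributed fractions and multinomial draws gives about 91 to 85% (n=360) and 89 to 80% (n=720).

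**6. Effect of weighting.** In simulation under the same assumptions, site-specific shares weighted to caseload, with stratified standard errors, restore coverage to about 93 to 96% at nearly the same width.

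**7. Proportional enrollment, sites fixed.** The ratio of stratified to binomial variance is [Σmᵢpᵢ(1−pᵢ)/N]/[p(1−p)]: Kaposi sarcoma 0.90, HPV-related 0.93, hematologic and other solid tumors 0.96. Here the stated intervals are slightly conservative.

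**8. A claim about all domestic sites.** ANOVA intraclass correlations (ICCs) from Table 10-B are 0.095 (Kaposi sarcoma), 0.059 (HPV-related), 0.025 (other solid) and 0.024 (hematologic). With caseloads scaled to n=720, Σm²/Σm = 85.2 × 720/763 = 80.4. The design effect is 1 + 79.4 × ICC = 8.6, 5.7, 3.0 and 2.9 if sites are a sample from a wide population. If 16 of an assumed 19 sites open, 1 + (design effect − 1) × 3/19 gives 2.2, 1.7, 1.3 and 1.3, and the Kaposi sarcoma half-width goes from 2.3 to about 3.4 points.

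**The case against.** The strongest reply is that the target is a named network. With the participating sites fixed they are strata, and step 7 shows that the binomial intervals are then not too narrow. This stands, provided enrollment is proportional to caseload. A reader might infer from the site differences that the error bars are simply too narrow, with a nominal 5% error of 25 to 50% at n=720. That needs the sites to be random draws from a wider population, which the documents do not say.

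A reader might also infer that the HACM comparison will produce false differences. The documents do not support this either. No test or decision rule is named, and the Table 10-B mix already differs from HACM (Kaposi sarcoma 18.2 against 10.9%, HPV-related 22.1 against 12.5%, other solid 32.1 against 49.3%). Even with the largest design effects at n=720, z is 2.2, 3.3 and −5.3; for hematologic cancers it is 0.1.

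Three further points are fair:
- The binomial interval is a planning calculation. The stated analysis interval is Poisson, and a sum of independent Poisson site counts is still Poisson, so differing site rates alone do not invalidate it.
- Table 10-B holds survey estimates, many of them round. Without the two high Kaposi sarcoma sites, that ICC drops from 0.095 to 0.038.
- The screening list exists to show which cancers present, so it could remove the problem. It would if it supplied the percentages. But Section 10 never mentions it, sizes the shares on enrolled numbers, and frames its monthly example as participants enrolled.

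**Conclusion.** The concern holds in a limited form. The plan does not protect the pooled mix, or its comparison with HACM, against uneven enrollment across sites whose mixes differ greatly. The loss is moderate: about 4 to 10 points of coverage for Kaposi sarcoma at n=360 and 6 to 15 points at n=720, and greater at the larger sample. It rests on the assumed CV of 0.3 to 0.5, on Table 10-B as the true site mixes, and on the participating sites as the target. With proportional enrollment the loss disappears.

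Whether the intervals should also be widened for sites that do not open depends on a target the plan leaves loose: the objective names domestic AMC sites, while the goal is to open at three quarters or more of them. The total number of domestic sites is not given, so the design effects of 1.3 to 2.2 are conditional on an assumed 19.

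**What to change.** In Section 10.1.2, estimate each cancer-type share as site-specific shares weighted to the site's screening-list caseload, with stratified standard errors, or take the mix directly from the screening list. Use that estimate for the HACM comparison. State in Sections 10.1.2 and 10.2.1 that the intervals apply to the participating sites. The list and the enrolled data should use the same case definition, since Section 8.1 limits the list to histologically confirmed cancer and Section 3.1.3 does not.

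If a claim about all domestic AMC sites is kept, add as a sensitivity analysis a site-clustered interval with a finite-population correction. Note under Table 10-A that its half-widths would then be wider, with the design effects above and the number of domestic sites stated.

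The cost is a few sentences and slightly more analysis. No new data or participants are needed, because cancer type is already on the list and Section 8.1 already compares the list with enrollment at each site. The downside is slightly wider intervals when enrollment is uneven.
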